10.1.3.4 Visit 7 (Week 24, Day 168 ±3, end of double-blind treatment period)

The following procedures/assessments will be performed at Visit 7.

- Physical examination including vital signs (systolic blood pressure [SBP] and diastolic blood pressure [DBP] in sitting position, heart rate in sitting position)
- Body weight
- Height without shoes
- Tanner stage
- Compliance check of IMP and data collection on IMP administration
- Concomitant medication recording
- Check of stability of background LMT
- Review of diet
- Collect AEs
- Cogstate battery test
- Fasting blood sampling for:
 - Total-C, LDL-C, HDL-C, TG, non-HDL-C
 - Apo B, Apo A-1, ratio Apo B/Apo A-1, and Lp(a)
 - Hematology and chemistry
 - HbA_{1c}
 - Creatine phosphokinase
 - Liver panel
 - Hs-CRP
 - CPK-MB, troponin
 - Adrenal gland hormones
 - Gonadal and pituitary hormones
 - Fat soluble vitamins
 - Anti-alirocumab antibodies (ADA)
 - Serum alirocumab concentration (Pharmacokinetics)
- Urinalysis
- Pregnancy test

- IRT contact to document end of double-blind treatment for patient not continuing in the open label part
- Flow mediated dilatation assessment only for patient included in the sub-study.

In addition, for patients continuing into the open label part, the following procedures/assessments will be performed:

- IRT contact
- Open label IMP kit dispensation
- IMP administration

10.1.4 Eighty-week open label treatment period

After patients successfully complete the 24-week double-blind treatment period, they can enter the open label treatment period which consists of 80 weeks of open label alirocumab.

The first open label alirocumab injection will be done at the site followed by monitoring of the patient for at least 30 minutes. The patient's regimen will be a continuation of their regimen from the double-blind treatment period. The dose of alirocumab may be adjusted based on patients body weight (ie, patients who previously were with BW <50 kg can be dose adjusted if their weight is \geq 50 kg) at each study visit starting from the first visit (ie, Week 24) of the open label treatment period. For patients whose weight varies close to 50 kg the dose will be adjusted only once at the onset of the open label treatment period.

The lipid levels will be communicated to the Investigator during the open label treatment period from the second visit (ie, Week 32) onwards. The Investigator will be responsible, based on his/her own judgment related to the patients' LDL-C levels and the safety profile, to up-titrate, down-titrate, maintain the dose of alirocumab or discontinue throughout the study. The statin dose should not be decreased to adjust to the degree of LDL-C lowering and should not be increased; unless otherwise indicated. Other LMT (if applicable) can be modified based on the Investigator's judgment throughout the study. Further recommendations for the management and monitoring of patients who achieve LDL-C levels <50 mg/dL (1.30 mmol/L) on one or more occasion are provided in the protocol.

10.1.4.1 Visit 8 (Week 32, Day 224 ±7)

The following procedures/assessments will be performed at Visit 8:

- Body weight
- IRT contact
- Compliance check of IMP and data collection on IMP administration
- Concomitant medication recording
- Check of stability of background LMT

Amended Clinical Trial Protocol 03 EFC14643 - alirocumab 06-Jan-2021 Version number: 1

- Review of diet
- Collect AEs
- Vital signs
- Fasting blood sampling for:
 - Total-C, LDL-C, HDL-C, TG, non-HDL-C
 - Hematology and chemistry
 - Creatine phosphokinase
 - Liver panel
- Pregnancy test
- Open label IMP kit dispensation
- IMP administration

10.1.4.2 Visit 9 (Week 44, Day 308 ±7)

The following procedures/assessments will be performed at Visit 9:

- Physical examination including vital signs (systolic blood pressure [SBP] and diastolic blood pressure [DBP] in sitting position, heart rate in sitting position).
- Body weight
- Height without shoes
- Tanner stage
- IRT contact
- Compliance check of IMP and data collection on IMP administration
- Concomitant medication recording
- Check of stability of background LMT
- Review of diet
- Collect AEs
- Vital signs
- Fasting blood sampling for:
 - Total-C, LDL-C, HDL-C, TG, non-HDL-C
 - Hematology and chemistry
 - Creatine phosphokinase (CPK)
 - Liver panel
 - Adrenal gland hormones

- Gonadal and pituitary hormones
- Fat soluble vitamins
- Pregnancy test
- Open label IMP kit dispensation
- IMP administration

10.1.4.3 Visit 10 (Week 56, Day 392 ±7, telephone contact)

The following procedures/assessments will be performed remotely at Visit 10:

- IRT contact
- Open label IMP kit delivery DTP (if applicable)
- Concomitant medication recording
- Check of stability of background LMT
- Review of diet
- Collect AEs
- IMP administration

10.1.4.4 Visit 11 (Week 68, Day 476 ±7)

The following procedures/assessments will be performed at Visit 11:

- Physical examination including vital signs (systolic blood pressure [SBP] and diastolic blood pressure [DBP] in sitting position, heart rate in sitting position).
- Body weight
- Height without shoes
- Tanner stage
- IRT contact
- Compliance check of IMP and data collection on IMP administration
- Concomitant medication recording
- Check of stability of background LMT
- Review of diet
- Collect AEs
- Vital signs
- Cogstate battery test
- Fasting blood sampling for:

- Total-C, LDL-C, HDL-C, TG, non-HDL-C
- Hematology and chemistry
- HbA_{1c}
- Creatine phosphokinase
- Liver panel
- Adrenal gland hormones
- Gonadal and pituitary hormones
- Fat soluble vitamins
- Anti-alirocumab antibodies (ADA)
- Pregnancy test
- Open label IMP kit dispensation
- IMP administration

10.1.4.5 Visit 12 (Week 80, Day 560 ±7, telephone contact)

The following procedures/assessments will be performed remotely at Visit 12:

- IRT contact
- Open label IMP kit delivery (DTP) (if applicable)
- Concomitant medication recording
- Check of stability of background LMT
- Review of diet
- Collect AEs
- IMP administration

10.1.4.6 Visit 13 (Week 92, Day 644 ±7)

The following procedures/assessments will be performed at Visit 13:

- Body weight measurement
- IRT contact
- Compliance check of IMP and data collection on IMP administration
- Open label IMP kit dispensation
- Concomitant medication recording
- Check of stability of background LMT
- Review of diet

Amended Clinical Trial Protocol 03 EFC14643 - alirocumab 06-Jan-2021 Version number: 1

- Collect AEs
- Pregnancy test
- IMP administration

10.1.4.7 Visit 14, End of Treatment (Week 104, Day 728 ±7)

The following procedures/assessments will be performed at Visit 14:

- Physical examination including vital signs (systolic blood pressure [SBP] and diastolic blood pressure [DBP] in sitting position, heart rate in sitting position)
- Body weight
- Height without shoes
- Tanner stage
- Compliance check of IMP and data collection on IMP administration
- Concomitant medication recording
- Check of stability of background LMT
- Review of diet
- Collect AEs
- Vital signs
- Cogstate battery test
- Fasting blood sampling for:
 - Apo B, Apo A-1, ratio Apo B/Apo A-1, and Lp(a)
 - Total-C, LDL-C, HDL-C, TG, non-HDL-C
 - Hematology and chemistry
 - HbA_{1c}
 - Creatine phosphokinase (CPK)
 - Liver panel
 - Adrenal gland hormones
 - Gonadal and pituitary hormones
 - Fat soluble vitamins
 - Anti-alirocumab antibodies (ADA)
- Pregnancy test
- IRT contact to document end of open label treatment

10.2 DEFINITION OF SOURCE DATA

Evaluations that are reported in the e-CRF must be supported by appropriately signed identified source documentation related but not limited to the following:

- Agreement, date, and signature of informed consent mentioning the study identification.
- Patient identification, last participation in a clinical trial, medical history, associated diseases, and data related to the studied pathology.
- Contraception methods for females of childbearing potential who are sexually active.
- Previous and concomitant medication (including the lipid modifying therapy).
- Study identification.
- Treatment number, dates of administration.
- Dates of visits and assessments including the examination report.
- Vital signs, height, body weight, Tanner stage.
- Faxed central lab reports (dated and signed by the Principal Investigator or Sub-Investigator).
- IRT confirmation fax (run-in, screening, screen failure, randomization, treatment (re)allocation, discontinuation, end of double-blind treatment period, end of open label treatment period, dose change alert).
- Adverse events and follow-up:
 - In case of SAE, the site should file in the source document at least copies of the hospitalization reports and any relevant examination reports documenting the follow-up of the SAE.
- Date of premature study discontinuation (if any) and reason.

Source documentation may be found in the following:

- Patient's identity.
- Medical history.
- Hospital records.
- Nursing notes.
- Physician's notes.

10.3 HANDLING OF PATIENT TEMPORARY OR PERMANENT TREATMENT DISCONTINUATION AND OF PATIENT STUDY DISCONTINUATION

The IMP should be continued whenever possible. In case the IMP is stopped, it should be determined whether the stop can be made temporarily; permanent IMP discontinuation should be

a last resort. Any IMP discontinuation must be fully documented in the e-CRF. In any case, the patient should remain in the study as long as possible.

Pregnancy will lead to definitive treatment discontinuation in all cases.

10.3.1 Temporary treatment discontinuation with investigational medicinal product(s)

Temporary treatment discontinuation (also referred to as treatment interruption) may be considered by the Investigator because of suspected AEs. Reinitiating of treatment with the IMP will be done under close and appropriate clinical/and or laboratory monitoring once the Investigator will have considered according to his/her best medical judgment that the responsibility of the IMP in the occurrence of the concerned event was unlikely and if the selection criteria for the study are still met (refer to Section 7.1 and Section 7.2). All treatment interruption duration must be recorded by the Investigator in the appropriate e-CRF screens when considered as confirmed.

Treatment interruption is defined as one or more scheduled injections that are not administered to the patient as decided by the Investigator.

10.3.2 Permanent treatment discontinuation with investigational medicinal product(s)

Permanent treatment discontinuation is any treatment discontinuation associated with the definitive decision from the Investigator not to re-expose the patient to the IMP at any time during the study, or from the patient not to be re-exposed to the IMP whatever the reason.

10.3.3 List of criteria for permanent treatment discontinuation

The patients may withdraw from treatment with the IMP if they decide to do so, at any time and irrespective of the reason, or this may be the Investigator's decision. All efforts should be made to document the reasons for treatment discontinuation and this should be documented in the e-CRF.

Patients should discontinue the IMP for the following reasons:

- Pregnancy, intention for pregnancy, or no longer with effective contraceptive method of birth control (females of childbearing potential who are sexually active only).
- Acute injection reaction of clinical concern.
- Serious adverse event (or non-serious but severe in intensity) of hypersensitivity reaction considered related to alirocumab.
- At patient/parents request (ie, withdrawal of the consent for treatment).
- If, in the Investigator's opinion, continuation with the administration of the IMP would be detrimental to the patient's well-being.
- Intercurrent condition that requires discontinuation of the IMP.
- At the specific request of the Sponsor.
- Patient receives treatment prior to randomization.

Any abnormal laboratory value will be immediately rechecked for confirmation (within 24 hours if possible), before making a decision of discontinuation of the IMP for the concerned patient

Any code-breaking requested by the Investigator will lead to permanent treatment discontinuation.

All cases of permanent treatment discontinuation must be recorded by the Investigator in the appropriate pages of the e-CRF when considered as confirmed.

10.3.4 Handling of patients after permanent treatment discontinuation

In case of permanent treatment discontinuation, the recommendation is to limit the collection to critical data, ie, primary endpoint/main secondary endpoint and safety endpoints.

Patients who prematurely discontinue study treatment (regardless of the reason) should undergo the following visits:

Premature treatment discontinuation during the double-blind treatment period:

- At the time of treatment discontinuation, the patient should have, as soon as possible, an unscheduled visit with assessments normally planned at end of treatment period visit including lipids, PK and ADA.
- Week 24 visit, as described in Section 1.3, should be performed regardless of timing of the last alirocumab injection, including for patients included and not treated.

All efforts should be done to perform these assessments.

Premature treatment discontinuation during the open label treatment period:

- At the time of treatment discontinuation, the patient should have, as soon as possible, an unscheduled visit with assessments normally planned at end of open label treatment period visit including lipids and ADA.
- Week 104 visit, as described in Section 1.3, should be performed regardless of timing of the last alirocumab injection.

Whatever the period of premature treatment discontinuation, the patient, at a minimum, should be followed up for recovery or stabilization of any AE as specified in this protocol.

All definitive discontinuation of study treatment should be recorded by the Investigator in the appropriate screens of the e-CRF and in the patient's medical records when considered as "confirmed". IRT should be notified when a patient prematurely discontinues study treatment.

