9 ASSESSMENT OF INVESTIGATIONAL MEDICINAL PRODUCT

9.1 PRIMARY ENDPOINT

9.1.1 Primary efficacy endpoint

Percent change in LDL-C from baseline to Week 24 in the intent-to-treat (ITT) population, using all LDL-C values regardless of adherence to treatment (ITT estimand).

The LDL-C at Week 24 will be the LDL-C level obtained within the Week 24 analysis window. All calculated and measured LDL-C values (scheduled or unscheduled, fasting or not fasting) may be used to provide a value for the primary efficacy endpoint if appropriate according to above definition. In case both calculated and measured LDL-C are provided for the same sampling, the measured LDL-C will be considered. The analysis window used to allocate a time point to a measurement will be defined in the SAP.

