9.2 SECONDARY ENDPOINTS

9.2.1 Key secondary efficacy endpoints

- Percent change in LDL-C from baseline to Week 12 (ITT estimand).
- Percent change in Apo B from baseline to Week 24 (ITT estimand).
- Percent change in non-HDL-C from baseline to Week 24 (ITT estimand).
- Percent change in Total-C from baseline to Week 24 (ITT estimand).
- Percent change in Apo B from baseline to Week 12 (ITT estimand).
- Percent change in non-HDL-C from baseline to Week 12 (ITT estimand).
- Percent change in Total-C from baseline to Week 12 (ITT estimand).
- Proportion of patients achieving a LDL-C level lower than 130 mg/dL (3.37 mmol/L) at Week 24 (ITT estimand).
- Proportion of patients achieving a LDL-C level lower than 130 mg/dL (3.37 mmol/L) at Week 12 (ITT estimand).
- Proportion of patients achieving a LDL-C level lower than 110 mg/dL (2.84 mmol/L) at Week 24 (ITT estimand).
- Proportion of patients achieving a LDL-C level lower than 110 mg/dL (2.84 mmol/L) at Week 12 (ITT estimand).
- Percent change in Lp (a) from baseline to Week 24 (ITT estimand).
- Percent change in Lp (a) from baseline to Week 12 (ITT estimand).
- Percent change in HDL-C from baseline to Week 24 (ITT estimand).

- Percent change in fasting TG from baseline to Week 24 (ITT estimand).
- Percent change in Apo A-1 from baseline to Week 24 (ITT estimand).
- Percent change in HDL-C from baseline to Week 12 (ITT estimand).
- Percent change in fasting TG from baseline to Week 12 (ITT estimand).
- Percent change in Apo A-1 from baseline to Week 12 (ITT estimand).

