In addition, these missing data are often intermittent, ie, followed by LDL-C values collected at subsequent visits. It is therefore considered reasonable to assume that these missing data were "At Random".

• Phase 2 studies DFI11565 and R727-CL-1003 included a prospective assessment of calculated LDL-C during the follow-up period after a 12-week treatment period. These studies showed that after treatment discontinuation, the average calculated LDL-C returned

to baseline level within 4 weeks after ceasing alirocumab treatment (See Figure 3 and Figure 4).

Figure 3 - Study DFI11565: calculated LDL-C mean (+/- SE) percent change from baseline

Figure 4 - Study R-727-CL-1003: calculated LDL-C mean (+/- SE) percent change from baseline

For each dosing regimen cohort, missing LDL-C values will be imputed 100 times to generate 100 complete data sets. The percent change from baseline to Week 24 will be derived from observed and imputed LDL-C at this time point. The completed data sets will be analyzed using a linear

Property of the Sanofi Group - strictly confidential

Statistical Analysis Plan SAR236553/RGN727-EFC14643 - alirocumab 19-Feb-2021 Version number: 2

regression model with the baseline LDL-C value as continuous covariate. Combined mean with their corresponding standard errors (SEs) and 97.5% CIs will be provided through the SAS MIANALYZE procedure using Rubin's formulae (8).

Imputation of missing data during the on-treatment period

Missing LDL-C values during the on-treatment period will be imputed from other on-treatment measurements assuming Missing At Random, using SAS MI procedure.

Only LDL-C values collected during the on-treatment period will be included in the imputation model. This way, missing LDL-C values during the on-treatment period will be imputed based solely on observed on-treatment LDL-C values.

The imputation model will include the baseline LDL-C value and all LDL-C values at pre-specified visits. Since the pattern of missing data is necessarily non-monotone, a Monte-Carlo Markov Chain (MCMC) method is used. A minimum value of 0 will be specified in order to avoid negative imputed LDL-C values.

A sample SAS code is provided below:

proc mi data=DATAIN out=DATAOUT nimpute=100 minimum=0;

var LDL_BASE LDL_W8 LDL_W12 LDL_W24 ;

run;

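### Patients who stop treatment before the Week 12 window opens have no required Week 12 lipid sample, although 10 of the 19 key secondary endpoints are Week 12 values under the ITT estimand

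*Protocol*

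**What the plan says.** Protocol 10.3.4 governs follow-up after permanent discontinuation. It states that "Patients who prematurely discontinue study treatment (regardless of the reason) should undergo the following visits" and, for the double-blind period, lists two:

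- "At the time of treatment discontinuation, the patient should have, as soon as possible, an unscheduled visit with assessments normally planned at end of treatment", with lipids named explicitly;
- "Week 24 visit, as described in Section 1.3, should be performed regardless of timing of the last alirocumab injection".

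The same section says that "the recommendation is to limit the collection to critical data, ie, primary endpoint/main secondary endpoint and safety endpoints". It does not say which endpoint is the main secondary one. Sections 10.3 and 10.3.5 encourage patients to remain in the study and leave the choice of key visits to discussion; neither names Week 12.

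Protocol 9.2.1 and SAP 2.1.3.2.1 list 19 key secondary endpoints, all under the ITT estimand, which Protocol 9.1.1 defines for LDL-C as using values whatever the adherence. Percent change in LDL-C at Week 12 stands first and gates the other 18 (Protocol 11.4.2.3).

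SAP 2.5.4 sets the Week 12 window at Day 71 to at most Day 98. SAP 2.5.5 lets an unscheduled sample supply a time point if it falls in the window. Missing values are handled by the MMRM or by multiple imputation. A pattern-mixture sensitivity analysis covers the key continuous secondary endpoints expected to be normally distributed (SAP 2.4.4.2.1).

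**The concern.** An ITT estimand at Week 12 needs Week 12 values from patients who have already stopped. For those who stop early, the visit list does not ask for them. The main models then predict the missing values, in large part from patients still on drug in the same arm.

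The SAP does not believe that prediction when it reasons about stoppers. For the pattern-mixture model, Appendix C writes: "These studies showed that after treatment discontinuation, the average calculated LDL-C returned" to the baseline level within four weeks. On that basis it imputes post-treatment gaps around the patient's own baseline, except for COVID-19 discontinuations. If that is right, the main Week 12 estimates lean towards a larger alirocumab effect and fall somewhat short of their stated estimand. The first of these endpoints is the gate to all the others.

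**Working it through.** **Count.** The list in Protocol 9.2.1 has 19 items. Week 12 accounts for 10: LDL-C, Apo B, non-HDL-C, Total-C, LDL-C below 130 mg/dL, LDL-C below 110 mg/dL, Lp(a), HDL-C, TG and Apo A-1. The other 9 are Week 24.

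**Who is affected.** A stop visit on Day 71 to 98 can supply the Week 12 value. A stop visit on or before Day 70 cannot, and the next required visit is Week 24 (window Day 155 to 182).

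**The plan's own figures.** With 30 vs 15 patients, difference 30, SD 25 and two-sided alpha 0.025, the noncentrality is 30 / (25 × √(1/30 + 1/15)) = 3.79. On 43 df this gives 92.5% power, in line with the stated 92%. Also 150 × 0.85 = 127.5, the stated 128 or so.

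**How many.** The documents give no dropout rate before Week 12, only 15% over 2 years. Assuming a constant hazard over 104 weeks (728 days):

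- by Day 84: 1 − 0.85^(84/728) = 1.9%, about 2.8 of 150, or 0.9 of a 50-patient arm;
- by Day 70: 1 − 0.85^(70/728) = 1.6%, about 2.3 of 150.

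So about 83% of stops before Week 12 would precede the window.

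**Upper bound on the bias.** If a share f of the alirocumab arm has stopped, is back at baseline by Week 12, and is filled in as if still treated, the overstatement is at most f × effect:

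| Share f | Effect | Bound (points) |
|---|---|---|
| 1.9% (constant hazard) | 30 (design difference) | 0.6 |
| 6% (assumed, 3 of 50) | 30 | 1.8 |
| 6% (assumed) | 46 (Phase 2 Week 8 change, no control arm) | 2.8 |

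**Against the noise.** At the planned size the standard error is 25 × √(1/50 + 1/25) = 6.1 points. A 30-point difference is 30 / 6.1 = 4.9 standard errors. Removing 2.8 points leaves 27.2 / 6.1 = 4.5, still far beyond the normal critical value of 2.24 for alpha 0.025.

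**Sensitivity coverage.** The pattern-mixture analysis reaches 6 of the 10 Week 12 endpoints: LDL-C, Apo B, non-HDL-C, Total-C, HDL-C and Apo A-1. The two LDL-C thresholds, Lp(a) and TG have none. For the thresholds, SAP 2.4.4.2.3 counts post-treatment gaps as failures (except COVID-19 discontinuations), but only in the fallback used when logistic regression cannot be fitted.

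**The case against.** A reader might infer from the visit list that early stoppers are asked back only at Week 24, or that their Week 12 values are missing by design. The documents support neither. A stop visit with lipids is required and can count for Week 12 if drawn in the window, and nothing forbids the scheduled Week 12 sample. A site could fairly take Week 12 LDL-C, first in the hierarchy, to be the main secondary endpoint. What stands is narrower: the list is incomplete, the term is undefined, and the general retention wording does not secure the sample.

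It is also tempting to read share times effect as the bias itself. It is a ceiling. The MMRM and the imputation model use the patient's own values at other visits, and the off-treatment Week 24 sample is required. If the Week 12 and Week 24 residuals correlated at 0.5 to 0.8 with equal SDs (an assumption), an observed Week 24 value would shrink the bound by a factor of 1 − 0.5 to 1 − 0.8: 0.6 becomes 0.1 to 0.3, and 2.8 becomes 0.6 to 1.4. Apo B, Apo A-1 and Lp(a) have no scheduled Week 8 sample, so for them the help comes mainly from Week 24.

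Some patients who stop injections are not yet off treatment by the SAP's definition. A Q4W patient last dosed on Day 57 counts as on treatment to Day 57 + 35 = Day 92, beyond the Day 85 target. Protocol 9.2.4.1 also allows for residual effect up to 10 weeks, which tempers the four-week return to baseline. Both points shrink the affected group; neither removes it.

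**Conclusion.** The gap is real and narrow. Patients whose stop visit falls before Day 71 have no required sample in the Week 12 window, and ten confirmatory endpoints claim an estimand that calls for one. The emergency measures in Protocol Appendix K list Week 12 lipids among the data to collect remotely, so the sample is evidently thought worth protecting.

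The possible bias is towards alirocumab, at most about 0.6 points on Week 12 LDL-C under the plan's own inputs and 2.8 under the harshest case above. This rests on a constant dropout hazard or an assumed 6%, full return to baseline by Week 12, and no information from other visits. A reader might infer that a test could reverse, or that the primary result is compromised. The arithmetic makes the first unlikely for LDL-C. The documents give no effect or SD for the other nine endpoints, but in a mean difference the overstatement is at most about f / (1 − f) of the ITT effect (6.4% at f = 6%), which matters only for a result near the boundary. The second does not follow, because the Week 24 visit is required of every stopper. This is a cheap improvement in the data behind the Week 12 endpoints, not a threat to the trial's conclusion.

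**What to change.** - **Protocol 10.3.4:** add that patients who stop double-blind treatment before Week 12 keep the already scheduled Week 12 lipid sample (panels 1 and 2). Alternatively, define the main secondary endpoint so that it includes the Week 12 lipids.
- **SAP 2.4.4.2.2 and 2.4.4.2.3:** add a sensitivity analysis equivalent to the pattern-mixture model for the four uncovered Week 12 endpoints. The two LDL-C thresholds can be derived from the imputed data sets already planned for Week 12 LDL-C. For Lp(a) and TG, impute post-treatment gaps around baseline before the robust regression, and state that return to baseline is an assumption there, since Appendix C's evidence concerns LDL-C only.

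The cost is one scheduled fasting sample kept in a few children who have stopped treatment, a line of protocol wording, and a little more analysis. For patients already past Week 12, only the SAP change can help.
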